# Pilot trial protocol template (includes a control group)

**Evaluating institution: University of Kent** 

**Principal investigator(s): [name]** 

Project title 	Re-Frame: Randomised Controlled Trial of a Diversion Programme for Adolescents in Police Custody who Possess Illicit Substances	
Developer (Institution)	We Are With You	
Evaluator (Institution)	University of Kent	
Principal investigator(s)	[name]	
Evaluation plan author(s)	[name]	
Evaluation setting	Community	
Target group	10-17 year olds, found in possession of class B or C illicit substances by police	
Number of participants	4 geographical areas, 96 participants	

# **Protocol version history**

<sup>1 Please make sure the title matches that in the header and that it is identified as a randomised trial as per the CONSORT requirements (CONSORT 1a).

Version	Date	Reason for revision
1.0 [original]	10/02/22	

Any changes to the design need to be discussed with the YEF Evaluation Manager (EM) and the developer team prior to any change(s) being finalised. Describe in the table above any agreed changes made to the evaluation design, research questions and approach, and the rational for these.

# Intervention

The relationship between substance use and criminal activity is complex but the prevalence of substance use is higher in adolescent offending populations and the two are related in the context of other forms of disinhibitory behaviour, such as aggression and risktaking(Wilson, 2013). Adolescents who offend experience a range of complex risks and vulnerabilities including neglect and abuse, substance use related problems, and exclusion from education (Newbury-Birch et al., 2015). As a group, they are more likely to experience health and social inequalities in later life. There is a widespread consensus that adolescents who offend are one of the most vulnerable and 'hard to reach' groups. Diversion from the CJS is a key window of opportunity whereby young people can reflect on their drug use and receive a brief intervention they might otherwise never receive. Brief psychosocial interventions delivered using a motivational interviewing approach within a FRAMES paradigm have been shown to be effective in adolescent (Steele et al., 2020; Winters and Leitten, 2007) and offer an opportunity to allow structured reflection on substance use and identify strategies to enhance self-efficacy, manage expectancies and motivation to change. The FRAMES approach (Rollnick et al., 2008) highlights six key aspects of behaviour change interventions; providing feedback on the relationship between substance use and behaviour, identifying the individual as being responsible for change, offering advice and managing ambivalence, providing a menu of options for change, being supportive and empathetic and enhancing the individuals self-efficacy.

As part of a comprehensive evaluation, the key aspects of the proposed study go beyond whether the intervention approach works to explore who it works for, how it works and how it could be implemented into routine practice.

## **Intervention Group**

Two sessions of Brief Intervention by skilled youth workers. In session one they will use a Drug Grid to reflect on how their actions have affected their lives, their family and wider community. The child will have the opportunity to recall their arrest experience and explain how this impacted them. The practitioner will assist the young person in critically reflecting on this event and offer support in relation to trauma or consequences felt as a result of it.

The Drug Grid is a drug education exercise that enables the child to demonstrate current understanding of substances (including medication, legal highs, and image and performance enhancing drugs). As they go through the exercise they will learn about these substances (eg depressant or hallucinogen), being led by their own experience and building on their knowledge base. The worker can dispel myths and provide information on the effects of each substance, including the risks of poly use and overdose.

Brief intervention session two is the Drug Triangle. With You will aim to complete this session within two weeks of the original referral. Ideally session one will take place in week one and session two in week two, depending on the child's availability and preferences.

Using the Drug Triangle, the child will focus on the substance, mindset and setting that led them to the session. This holistic harm reduction approach ties in with contextual safeguarding, framing the child's situation within a wider context. They will spend time thinking about how this has affected them, their family, school (if applicable), and community. The child will also be encouraged to reflect on the impact on those people and communities that produce drugs. At the end of the session the participant will be advised around their rights in relation to stop and search procedures should they require it in the future as well as assertion techniques and advice relating to the procedure itself.

At the end of the two sessions the young person will have greater clarity about the risks they have taken, the links between substance use, risk-taking behaviour and violent offending and the potential of criminal proceedings. The short-term aims are that the child will have a greater understanding of their personal needs, increase in confidence to reduce substance use, and a positive shift from precontemplation to action and maintenance in the cycle of change.

# **Control Group**

The child will receive one session of Advice, Information and Signposting. The child will be offered information about the With You substance service in their local area and encouraged to access the service for support if required. Advice, Information and Signposting is a tier 1, universal level of support. It is unstructured and is based on a conversation only.

### **Re-Frame: Logic Model**

### Objectives

Reduce the frequency of substance use in a population of young people arrested by the police and found in possession of illicit substances.

Reduce the frequency of offending in this population.

Improve knowledge of the link between substance use and risk taking.

Improve wellbeing, quality of life, and improve health.

Enable them to engage in education and prosocial activities.

### Input/ Resources

## Staff

-Highly dedicated to working with young people -Qualified with Gateway level 3: tackling substance misuse -Sensitive to the needs of the client group -Similar to client group demographically and culturally -In receipt of ongoing supervision

Partnership

-Relationship with police -Relationship with other stakeholders such as mental health, social services and early intervention

#### Activities

#### Referral

Eligible young people referred by police for second chance diversion, creates a window of opportunity.

#### Drugs Grid

Delivered in a single 45 minute session. This provides education regarding drugs, their effects on physical and mental health and the law. Allows exploration of knowledge, expectancy and risks and feedback concerning individual risk profile.

### Drug Triangle

delivered in a single session over 45 minutes. Focus on contextual safeguarding and explores the impact of substance use on the individual, family and network. Explores the relationship between perceived and actual expectancy, increases confidence and enhances motivation.

#### **Extended Access**

Access to other drug and mental health services and signposting towards prosocial opportunities.

### Short term outcomes (Process)

#### Staff

-All staff trained in delivering the interventions -Staff meet regularly to share learning and receive supervision and work towards higher qualifications.

#### **Young People**

-Young people given a second chance and diverted out of CJS -Of those arrested are offered a meaningful intervention -80% of those offered the intervention engage with both elements

### Intermediate outcomes

Among young people who receive the intervention versus those that do not there will be

-a significant reduction in the frequency of substance use

- a significant reduction in offences

-increased wellbeing and quality of life

-better emotional regulation

-increased confidence to resist substance use

-increased motivation to maintain change

### Long term outcomes

[figure not shown]
Sustained reduction in offences and substance use.

Improved wellbeing and quality of life.

Greater engagement in education and/or work. Increased engagement in prosocial activities.

[figure not shown]
Fewer family and peer related problems.

### **Re-Frame: Blueprint**

### **TEMPLATE: THEORY OF CHANGE**

### **Re-Frame: Theory of Change**

# Primary outcome measures

Our primary outcome is all offences; including arrests, cautions and charges, in the 6months post randomisation obtained directly from the Police National Computer. In addition to the primary outcome this will allow us to extract data for the period 6 months prior to randomisation as a covariate and other outcomes including all offences and specific substance use offences as secondary outcomes. Secondary outcomes are listed in detail below..

# Research questions and/or objectives

# Objectives of the pilot trial

1. To pilot study outcomes and evaluation methods, assess the parameters for conducting an efficacy evaluation and to assess whether operational progression criteria have been met and if so to develop a full protocol for an appropriately powered efficacy study.

2. To assess the acceptability of an ethically appropriate standardised business as usual control.

3. To qualitatively explore the feasibility and acceptability of referral pathways, intervention delivery and study assessments from the perspectives of the police, intervention provider and participants. A key aim is to identify how, when, why and for whom the interventions work.

# Success criteria and/or targets

In the pilot phase of the study we will estimate likely proportions of participants who are eligible, who consent, adhere to the intervention and the proportion followed-up at 6 months. Proportions will be compared to predefined progression criteria.

Criteria			
Proportion referred who are eligible	70%	50%	40%
Proportion eligible who consent	70%	50%	40%
Proportion eligible who adhere		60%	40%
Proportion followed-up (secondary)		70%	60%

Where progression criteria are green the efficacy study will continue as planned, if amber or red discussion regarding remedial action will be taken prior to embarking on the efficacy study.

In addition to proportions we will assess data completeness for each outcome instrument. A threshold of 60% complete will be used to assess whether an outcome instrument should be included in the efficacy trial.

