# Randomisation

Randomisation will employ random permuted blocks of variable size stratified by site; Kent, Cornwall, Sefton, Lancashire and by age group; 10-14 versus 15-17 years. Random strings will be created for each stratification combination and deployed independent of the research team and each participant will have equal probability of being allocated to the intervention or business as usual.

Randomisation will be conducted after eligibility has been assessed, informed consent provided and baseline assessment conducted. The researcher will enter necessary details into an encrypted database and after necessary data has been checked an allocation code will be provided. This code will indicate the nature of allocated group. The researcher will not be able to access randomisation codes. The participant will not be blind to the intervention.

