# **Data analysis**

In the pilot phase of the study we will estimate likely proportions of participants who are eligible, who consent and the proportion followed-up at 6 months. Each of these will be assessed against progression criteria agreed a priori.

We will conduct a descriptive analysis of outcomes including measures of central tendency and estimates of precision for continuous outcomes and proportions for categorical outcomes. Inferential analysis at the pilot stage will focus on the primary outcome, offences at 6-months with the aim of providing estimates of the potential effect of the intervention. After conducting diagnostic plots and selecting an appropriate regression approach, adjusting for baseline values and stratification variables as covariates, we will present the marginal effect, mean difference between the intervention and control groups and 80% confidence intervals. This analysis will allow us to confirm or revise our sample size calculation. At this stage we will also explore the pattern of missing data for each outcome and by key demographic indicators such as ethnicity and age, if missing data exceeds 40%, we will make judgements about whether to incorporate the outcome in the efficacy study.

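### The adherence progression criterion uses all eligible young people as its denominator, so for adherence to Re-Frame it cannot exceed half the consent rate and the printed 60% level is out of reach

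*Protocol*

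**What the plan says.** In the Protocol, Success criteria and/or targets, the text before the table lists the proportions to be compared with predefined criteria. Among them are those who "adhere to the intervention and the proportion followed-up at 6 months". The table row itself reads "Proportion eligible who adhere", with printed levels of 60% and 40%. The row above it, "Proportion eligible who consent", has levels of 70%, 50% and 40%. For results short of green, the section says that "if amber or red discussion regarding remedial action will be taken prior to embarking on the efficacy study".

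The Randomisation section fixes the order of steps: "Randomisation will be conducted after eligibility has been assessed, informed consent provided and baseline assessment conducted". It also fixes the ratio: "each participant will have equal probability of being allocated to the intervention or business as usual". The flow chart under Quantitative data collection shows that young people who do not consent receive treatment as usual.

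Other sections use other bases for adherence:
- The logic model (short-term outcomes, Young People) expects that "80% of those offered the intervention engage with both elements".
- Sample size promises 95% confidence intervals with half-widths under 0.15 for several proportions, adherence included, in each arm of 48.
- Outcome measures records attendance in the intervention and the control arm alike.
- Data analysis says "we will estimate likely proportions of participants who are eligible, who consent and the proportion followed-up at 6 months", which leaves adherence out.

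**The concern.** The word eligible appears in both the consent row and the adherence row, so on a plain reading both share one denominator: everyone found eligible, before consent. Two groups in that denominator can never attend the Re-Frame sessions, namely those who decline and those allocated to control. The criterion therefore multiplies together the consent rate, the allocation ratio and actual attendance, although it is meant to show only whether young people attend what they are offered.

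Judging whether the progression criteria are met is part of the pilot's first objective. With this denominator a fully attended intervention could not reach 60%, and poor consent would count against the trial in its own row and again under adherence. If analysts noticed the problem only after seeing the data and changed the denominator then, the criterion would no longer be predefined.

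**Working it through.** **Inputs from the Protocol.** Allocation 1:1 (Randomisation). 96 participants, 48 per arm (Sample size). Consent levels 70%, 50% and 40%; adherence levels 60% and 40% (Success criteria and/or targets). Engagement target 80% of those offered the intervention (logic model).

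**1. The plan's own precision figure.** Half-width = 1.96 × √(p(1 − p)/n), with n = 48. At the worst case, p = 0.5, this gives 1.96 × √(0.25/48) = 0.141. The Wilson interval gives 0.136 and the Clopper-Pearson interval 0.148. All are below 0.15, so the statement reproduces. For adherence it is a statement about a denominator of 48 in an arm, not about all eligible young people.

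**2. The criterion as worded, counting adherence to Re-Frame.** Let c be the consent rate among the eligible and a the attendance among those allocated to Re-Frame.

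Proportion of eligible who adhere = c × 0.5 × a, with maximum 0.5c at a = 1.

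| Consent c | Maximum (a = 1) | With a = 0.8 |
|---|---|---|
| 50% | 25% | 20% |
| 70% | 35% | 28% |
| 80% | 40% | 32% |
| 90% | 45% | 36% |
| 100% | 50% | 40% |

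- To reach 60% with perfect attendance: c = 0.60/0.5 = 1.20, that is 120% consent, which is impossible.
- To reach 40% with perfect attendance: c = 0.40/0.5 = 0.80. With 80% attendance: c = 0.40/(0.5 × 0.8) = 1.00.
- In counts at 70% consent: 96/0.70 ≈ 137 eligible, of whom 48 are allocated to Re-Frame; 48/137 = 35%.

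**3. The alternative reading, counting attendance in both arms.** Proportion = c × a.

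- At c = 0.70 the maximum is 70%. Reaching 60% needs a = 0.60/0.70 = 85.7%, and reaching 40% needs a = 0.40/0.70 = 57.1%.
- At c = 0.70 and a = 0.80 the value is 56%; at c = 0.80 and a = 0.80 it is 64%.

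The 60% level is attainable here, but the result still moves with the consent rate at fixed attendance.

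**4. With participants allocated to Re-Frame as the denominator.** The proportion can run from 0 to 100%.

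- 60% of 48 = 28.8, so 29 participants.
- 40% of 48 = 19.2, so 20 participants.
- Half-width at 60%: 1.96 × √(0.24/48) = 0.139. At 80%: 1.96 × √(0.16/48) = 0.113. Both are within the stated 0.15.

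**The case against.** The strongest reply is that this is a mislabelled row whose intent can be recovered. Sample size treats adherence per arm, the logic model uses those offered the intervention, and an analyst would probably compute attendance within an arm. That is fair as to intent and supports the correction proposed below. It does not rescue the row, because no section explains an eligible base for adherence and the table is where the decision rule is set.

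A second reply is that Outcome measures records attendance in both arms, so control attendance may count. That reading makes 60% attainable, and the point must allow for it. It sits poorly with the table's introduction, which speaks of the intervention, and it keeps consent inside the measure.

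A reader might go further and infer that a good consent rate forces a red result however well Re-Frame is attended. The Protocol does not support that. Taking red as below 40%, red is unavoidable only when consent is below 80%; from 80% to 100% consent the ceiling is 40% to 50%. The Risks section reports earlier recruitment of 80% of those potentially eligible, a rate at which the ceiling just equals 40%. The column headings and the first cell of the adherence row do not show in the text available for this review, so any assignment of colours is an assumption and the blank cell is not held against the plan.

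Nor does it follow that the progression decision would be wrong. Amber or red leads to discussion of remedial action, where a denominator artefact could well be noticed. The omission of adherence from Data analysis is best seen as an incomplete restatement, since other sections keep it.

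**Conclusion.** The point holds for the wording of the criterion. With eligible young people as denominator and adherence to Re-Frame as numerator, the proportion cannot exceed half the consent rate. The 60% level is unattainable at any consent rate, and at 70% consent the ceiling of 35% lies below the 40% level. The first conclusion does not depend on the colours: whether 60% or some higher figure in the blank cell is green, it lies above the 50% ceiling.

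This rests on two assumptions: that eligible means the same in the adherence row as in the consent row, and that adherence means attending Re-Frame. If both arms count, 60% can be reached, at 70% consent with 85.7% attendance, and the remaining fault is that low consent is counted a second time. The consequence is a misleading signal on adherence and an unnecessary remedial discussion, not an automatic stop.

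**What to change.** Redefine the row as the proportion of participants allocated to Re-Frame who attend both sessions, with those randomised to that arm (about 48) as denominator. Keep the printed thresholds, which become 29 of 48 for 60% and 20 of 48 for 40%. Report attendance at the control session separately, without a place in this criterion.

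Then make the related sections agree with this base: the logic model's engagement target, the description of adherence under Outcome measures, the per-arm precision statement in Sample size, and the list of proportions in Data analysis, to which adherence should be added.

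The top threshold should not be changed to the logic model's 80%. An expected outcome in a logic model need not be a progression threshold, and the first cell of the row cannot be seen here.

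The cost is one table row and a few sentences. Attendance is already to be recorded, so no new data, participants or analyses are needed. The change should be made before the criteria are applied to any data.

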# **Methods**

# **Pilot trial design**

Two-armed prospective individually randomised controlled internal pilot trial.

# Randomisation

Randomisation will employ random permuted blocks of variable size stratified by site; Kent, Cornwall, Sefton, Lancashire and by age group; 10-14 versus 15-17 years. Random strings will be created for each stratification combination and deployed independent of the research team and each participant will have equal probability of being allocated to the intervention or business as usual.

Randomisation will be conducted after eligibility has been assessed, informed consent provided and baseline assessment conducted. The researcher will enter necessary details into an encrypted database and after necessary data has been checked an allocation code will be provided. This code will indicate the nature of allocated group. The researcher will not be able to access randomisation codes. The participant will not be blind to the intervention.

# Participants

Participants will be referred by the police to existing we Are with You Young People's substance misuse services across four geographical areas of England; Kent, Sefton, Cornwall, Lancashire.

# **Eligibility criteria**

Inclusion Criteria: Aged 10-17 years inclusive Considered appropriate for diversion by police In possession of class B or C illicit substances

Exclusion Criteria:

# Arrested for a sexual or violent offence

History of four or more offences

Substance use severity that requires specialist clinical intervention such as detoxification or medication assisted maintenance

Inability to understand oral English sufficiently to engage in the intervention or the followup to the extent the participant requires an interpreter to engage with the intervention or research. Outcomes are validated for English language populations.

# **Outcome measures**

Our primary outcome is all offences; including arrests, cautions and charges, 6-months post randomisation obtained directly from the Police National Computer. In addition to the primary outcome this will allow us to extract data for the period 6 months prior to randomisation as a covariate and other outcomes including all offences and specific substance use offences as secondary outcomes. Frequency of substance use will be assessed at 6-months using the Time Line Follow Back Method (TLFB; (Levy et al., 2004; Sobell and Sobell, 1995)), a valid and reliable tool for assessing the frequency and quantity of substance use over time periods ranging from 1 to 365 days and validated specifically for adolescents (Levy et al., 2004). To minimise burden, we will use the 28-day version which takes about 10 minutes to complete and demonstrates an excellent level of agreement with longer versions. This tool allows us to derive the percent days abstinent from substance use and allows derivation of several other outcomes over the period (e.g., quantity and type of substances consumed). As there is evidence of assessment reactivity associated with TLFB in brief intervention studies we will only measure TLFB at 6-months and employ a single frequency of substance use question at baseline for inclusion in the analytical model as a covariate.

Mental health and wellbeing will be assessed using the Warwick-Edinburgh Mental Wellbeing scale (WEMWBS; (Clarke et al., 2011)). WEMWBS is a 14-item, self-completed scale addressing different aspects of eudemonic and hedonic mental health wellbeing. Healthrelated quality of life will be derived from a short assessment of health utility used extensively in this population (CHU-9D; (Stevens, 2012)).

Emotional regulation and behaviour will be assessed using the self-completed Strength and Difficulties questionnaire (SDQ; (Goodman, 1997)). This assesses behaviour across several domains, conduct, hyperactivity, emotional regulation, peer relationships and prosocial. Self-reported offending will be assessed using the Self-Report Delinquency Scale (SRDS; (Smith and McVie, 2003)) over the previous six months. All these instruments will be assessed at baseline and 6-months. To explore the process of change we aim to assess three domains that are key targets of brief interventions. Motivation to change will be assessed using the readiness to change ruler, a single question that assesses motivational stage in adolescents (RR; (Maisto et al., 2011)). Self-efficacy will be assessed using the short Situational Confidence Questionnaire (SCQ-8; (Breslin et al., 1998)). Positive and Negative Expectancy will be assessed using a fouritem expectancy measure (SUE; (Montes et al., 2019)). These instruments will be assessed at baseline and at the 6-month follow-up point and have established psychometric properties in the adolescent population.

In addition to key demographics, age, gender, ethnicity, age of first substance use, family structure that will be assessed at baseline we will use a number of short, validated instruments to assess potential predictors of change and identify potential subgroups within the study. These include a short assessment of family environment assessing relationships, conflict and cohesion the Brief Family relationship Scale (BFRS; (Fok et al., 2014)), anxiety using the General Anxiety Disorder Questionnaire (GAD-7; (Mossman et al., 2017)) and depression using the Personal Health Questionnaire for adolescents (PHQ-A; (Mansour et al., 2020)) and adverse child experiences using the Adverse Child Experience Questionnaire (ACEQ; (Dong et al., 2004)). All these instruments are validated for use in an adolescent population.

We will assess adherence by recording attendance at each element of the intervention and the control. For those in the intervention group we will assess fidelity by randomly recording 20% of brief intervention sessions stratified by age group, interventionist and site and independently score these using the Behavioural Change Counselling Index (BECCI; (Lane, 2002)). We will ask participants in the intervention arm to complete the short revised therapeutic alliance scale for children after the second intervention session (TASC-r; (Shirk and Saiz, 1992)). There is emerging evidence that the perceptions of interventionists play a key role in the quality of intervention delivered, particularly in terms of their perceived role legitimacy and self-efficacy, both targets of training and ongoing supervision. In order to assess these perceptions, we will ask interventionists to complete the Drug and Drug Using Populations Perceptions Questionnaire (DDPPQ; (Connors et al., 2019)) just prior to training and again 6-months after being trained.

All the outcome measures have been used previously in adolescent populations and we estimate the outcome data set takes on average 40 minutes to complete. We will assess burden in the pilot stage with a simple measure of cognitive burden. At the end of the pilot study, we will assess all instruments for data completeness and make informed decisions regarding their inclusion in the efficacy study.

Proposed outcomes at each stage of the evaluation

Outcome	No. of Questions	Baseline	Month 6
Frequency of substance use (Single TLFB item)	1	$\checkmark$	
Time Line Follow-Back 28-day version 	0		$\checkmark$
Wellbeing (WEBWMS)	14	$\checkmark$	$\checkmark$
Quality of Life (EQ5D-5L)	5	$\checkmark$	$\checkmark$
Strength & Difficulties (SDQ  )	25	$\checkmark$	$\checkmark$
Self-report Delinquency (SRDS  )		$\checkmark$	$\checkmark$
Motivation state to change (RR)	1	$\checkmark$	$\checkmark$
Substance Use Expectancy (SUE)	4	$\checkmark$	$\checkmark$
Self-efficacy (SCQ-8)	8	$\checkmark$	$\checkmark$
Generalised Anxiety Scale (GAD-7)	7	$\checkmark$	
Depression - Personal Health Questionnaire (PHQ-A)	8	$\checkmark$	
Adverse Childhood Experiences (ACEQ)	10	$\checkmark$	
Brief Family Relationships Questionnaire (BFRS)	16	$\checkmark$	

 $^1\,{\rm TLFB28}$  and SRDS are researcher led questionnaires rather than client self-completed  $^2\,{\rm SRDS}$  and SDQ are YEF Core outcomes

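### The primary outcome does not fix the counting unit or dating rule and does not exclude the index possession, so on a literal reading one offence can count twice and a late disposal of the index event counts as reoffending

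*Protocol*

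**What the plan says.** The primary outcome is defined twice. Outcome measures has: "Our primary outcome is all offences; including arrests, cautions and charges, 6-months post randomisation obtained directly from the Police National Computer". The earlier section, Primary outcome measures, has: "Our primary outcome is all offences; including arrests, cautions and charges, in the 6months post randomisation". I read both as a six-month window starting at randomisation.

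Both sections add that the same extract will supply a covariate for the six months before randomisation, and "other outcomes including all offences and specific substance use offences as secondary outcomes".

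Every participant enters through a police contact for drugs. The inclusion criterion is "In possession of class B or C illicit substances", and the logic model's Objectives describe "a population of young people arrested by the police and found in possession of illicit substances". Under Randomisation, allocation follows eligibility assessment, consent and baseline assessment. The index event therefore always precedes the outcome window.

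Data analysis makes offences at six months the focus of inference in the pilot. The result is a mean difference with an 80% confidence interval, used to confirm or revise the efficacy sample size.

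**The concern.** Arrest, caution and charge can be successive police records of one offence. The definition names all three as included and attaches the six-month window to them. It states no counting unit, no choice between offence date and record date, and no exclusion of the qualifying event.

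Two consequences follow from the literal wording. First, an incident that moves from arrest to charge can contribute two events, while one that stops at arrest contributes one. Second, if the index possession leads to a caution or charge recorded after randomisation, something done before the trial is counted as reoffending, and no intervention can prevent it.

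A separate fault lies in the text itself. All offences is the primary outcome and also appears among the secondary outcomes, with nothing to tell the two apart.

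At stake are the event rate, its variance and the mean difference that the pilot hands to the efficacy trial.

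**Working it through.** **The plan's own figure.** Sample size claims 95% half-widths below 0.15 for proportions with 48 per arm. At the worst case, 1.96 × √(0.5 × 0.5 / 48) = 0.141, so the claim is correct. It concerns proportions and does not depend on how offences are counted. The protocol gives no offence rate, so what follows rests on assumptions.

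**Double records.** Assume Poisson incidents with mean m, each giving two records with probability p and otherwise one.
- Mean count = m(1 + p).
- Variance = m(1 + 3p), since the mean squared score is (1 − p) + 4p.
- Variance-to-mean ratio = (1 + 3p)/(1 + p).
- The rate ratio between arms is unchanged. The mean difference is multiplied by 1 + p.
- N for a given rate ratio is multiplied by (1 + 3p)/(1 + p)².

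| p (assumed) | Mean multiplied by | Variance/mean | N multiplied by |
|---|---|---|---|
| 0 | 1.00 | 1.00 | 1.00 |
| 0.25 | 1.25 | 1.40 | 1.12 |
| 0.50 | 1.50 | 1.67 | 1.11 |
| 0.75 | 1.75 | 1.86 | 1.06 |

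**Late index disposals, equally frequent in both arms.** Assume 0.5 new incidents per control participant in six months, a true rate ratio of 0.70 (0.35 in the intervention arm), no double records, and a share q in each arm with one index disposal recorded after randomisation.
- Means are 0.5 + q and 0.35 + q, so the expected difference stays at 0.15.
- Variances are 0.5 + q(1 − q) and 0.35 + q(1 − q).
- n per arm for 80% power at two-sided 5% = 7.85 × (sum of variances) / 0.15².

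| q (assumed) | Observed rate ratio | Sum of variances | n per arm |
|---|---|---|---|
| 0 | 0.35/0.50 = 0.70 | 0.850 | 297 |
| 0.10 | 0.45/0.60 = 0.75 | 1.030 | 360 |
| 0.25 | 0.60/0.75 = 0.80 | 1.225 | 428 |
| 0.50 | 0.85/1.00 = 0.85 | 1.350 | 471 |

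With the control rate varied from 0.3 to 1.0, the observed ratio lies between 0.73 and 0.78 at q = 0.10, between 0.76 and 0.84 at 0.25, and between 0.80 and 0.89 at 0.50.

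The two mechanisms act differently. Double records inflate the mean difference and the dispersion but leave the ratio alone. Equal index carry-over leaves the expected difference alone, inflates the rate, adds variance, and pulls the ratio towards 1.

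**The case against.** The kinder reading is that the unit is the offence, and that arrests, cautions and charges merely list the police statuses by which an offence qualifies. Nothing says that records are summed, and the outcome could even be any versus none, since Data analysis leaves the regression approach open. This stands as far as it goes: the wording is ambiguous, and adding records is one reading of it. But the protocol does not write the kinder reading, and even that reading leaves open whether the index possession counts when its disposal falls inside the window.

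De-duplication and date fields are often left to an analysis plan, and Timeline lists one that is not at hand. That is fair for coding detail. The unit, the dating and the exclusion of the qualifying event decide what the primary outcome is, and the protocol states that definition twice without them.

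A reader might infer bias between arms: Re-Frame has two sessions and control one, so more Re-Frame participants might fail to complete diversion and be cautioned or charged. The documents do not support this. No section makes attendance a condition of diversion or attaches a police consequence to a missed session. The logic model says only "Eligible young people referred by police for second chance diversion" and "Young people given a second chance and diverted out of CJS". The mention of "the potential of criminal proceedings" describes what participants should understand after the sessions, not a sanction. Diversion may also make late disposals uncommon.

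If the efficacy trial kept the same counting rule, the pilot's mean and variance would be the right planning inputs for it, and double records would cost only efficiency. That also stands. It does not rescue the index carry-over, which would then weaken both stages. The effect on the covariate is small where each participant's one index event adds about the same constant.

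Finally, the progression criteria cover eligibility, consent, adherence and follow-up, so none depends on the offence count.

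**Conclusion.** The point holds as a defect in the definition of the primary outcome. On the literal wording, one offence can count twice and a post-randomisation disposal of the index possession would count as reoffending. The protocol does not show how often either happens.

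The size is therefore conditional: 6% to 12% on N if 25% to 75% of incidents give two records; and, at 0.5 incidents and a true ratio of 0.70, from 297 to between 360 and 471 per arm if 10% to 50% have a late index disposal. Both rest on Poisson incidents, and the second on equal frequency in the two arms. Under those conditions the harm is dilution of the ratio, added noise and unreliable planning inputs, not a tilt towards either arm.

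It should be settled before the police data are extracted, because this is the only outcome analysed inferentially and it feeds the efficacy sample size. The duplicated all-offences entry needs reconciling whatever the counting rule turns out to be.

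**What to change.** - Define the primary outcome as the number of distinct offences with an offence date after randomisation and within six months, each counted once whatever police records it generates.
- Exclude any record tied to the index possession, whenever it was made.
- State how the index event is treated in the prior six-month covariate, in the same way for everyone.
- Make sure the data-sharing agreements supply the offence date, so that records can be matched to offences.
- Reconcile the two all-offences entries: delete the secondary one or say how it differs. Which of them is the slip is for the sponsor to say. Substance-specific offences can stay as a secondary outcome.

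The cost is a change of wording and a small de-duplication and matching step on the same extract. No further data collection from participants is needed.
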